### **1.3 Exploratory Objectives**

1. To evaluate the response rate, EFS and OS in FLT3 mutated/NPM1 wild-type patients versus FLT3 mutated/NPM1 mutated versus FLT3 wild-type/NPM1 mutated patients treated with the combination of selinexor and sorafenib.
2. Quantitative changes of FLT3-ITD and –D835 allelic burden with time in patients treated with the combination of selinexor and sorafenib.
3. To evaluate the extent of pharmacodynamics biomarker (such as p-FLT3, p-p70S6K, pERK) inhibition and the induction of apoptosis in the bone marrow and peripheral blasts following treatment with the combination of selinexor and sorafenib.
4. To investigate possible relationships between selinexor and other baseline gene expression signatures and clinical response.
5. To store and/or analyze surplus blood or tissue including bone marrow, if available, for potential future exploratory research into factors that may influence development of AML and/or response to selinexor (where response is defined broadly to include efficacy, tolerability or safety).
6. To evaluate the pharmacodynamic effects of treatment on induction/inhibition of XPO1 using qRT-PCR and on plasma protein/cytokine levels.

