## 6.0 CORRELATIVE/SPECIAL STUDIES (Optional)

### 6.1 Effect of MAPK, AKT signaling and apoptosis induction

The timetable for collection of peripheral blood will be as defined in section 7.2 below.

Vectra testing will be done for p53, survivin, FLT3, pPI3K, pAKT, pERK. Reverse phase protein assay (RPPA) will be utilized to assess activation of FLT3, MAPK, AKT (via detection of phosphorylated FLT3, ERK, pS6, p4EBP1 and pAKT). We will analyze induction of apoptosis in AML stem cells by 3-color flow cytometry assay (CD34/annexin V/CMXRos) established in [name] laboratory. RT-PCR analysis on selected markers will be done only on bone marrow samples.

Peripheral blood for these studies (Vectra, 3-color flow, RPPA) will be collected prior to the first dose of selinexor (baseline: day 1) in cycle 1, 24 (+/- 4) hours post the first dose of selinexor in cycle 1, cycle 1 day 28 (+/- 7 days), and at progression/relapse (if available). Bone marrow samples for studies (Vectra, 3-color flow, RPPA, PCR) will be collected at baseline (within the last 7 days preceding the first dose of selinexor), cycle 1 day 28 (+/- 7 days), and at progression/relapse (if available). Correlative studies and biomarker evaluation will be performed by [name] lab.

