### 6.2 XPO1 induction/inhibition

Whole blood (2 tubes X 2.5 mL) will be obtained to assess XPO1 induction/inhibition in leukocytes prior to the first dose of selinexor and 4 hours (+/- 1) hours post the first dose of selinexor on cycle 1 day 1 only, by quantitative real time polymerase chain reaction (qRT-PCR). Karyopharm Therapeutics will be responsible for this testing. Karyopharm will also analyze a panel of additional genes as well as microRNA expression on the blood samples from these time points.

A Karyopharm Therapeutics laboratory manual (Appendix F) and supplies has been provided to facilitate testing. Sample collection and shipment details will be included in the laboratory manual.

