### 11.3 Statistical Analysis Plan

All patients who received any dose of the study agent will be included in the analysis for efficacy and safety. Demographic/clinical characteristics (including duration of response) and safety data of the patients will be summarized using descriptive statistics such as mean, standard deviation, median and range. For the primary efficacy analysis, we will estimate the ORR for the combination treatment, along with the 95% confidence interval. In addition, we will estimate composite CRc rate, partial response and marrow clearance rate within 3 months by FLT3 mutation. Patients who drop out of the study before completing all the cycles will be treated as “failures” for the primary analysis. ORR during the study period will also be presented with the 95% confidence interval. The association between ORR and patient’s clinical characteristics will be examined by Wilcoxon’s rank sum test or Fisher’s exact test, as appropriate. Toxicity type, severity and attribution will be summarized for each patient using frequency tables.

The distribution of time-to-event endpoints (DFS and OS) including overall survival and progression free survival will be estimated using the method of Kaplan and Meier. Comparisons of time-to-event endpoints by important subgroups will be made using the log-rank tests. Paired t-tests will be used to determine the immunological and molecular changes in the peripheral blood and bone marrow from baseline to the time of response, and to the time of disease progression.

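### The biomarker change tests in section 11.3 do not match the sampling schedule: the 4-hour and 24-hour samples have no usable planned test, and the response contrast selects on outcome

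*Combined protocol and SAP*

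**What the plan says.** **Planned test (section 11.3).** One sentence covers biomarker change. It assigns paired t-tests to "changes in the peripheral blood and bone marrow from baseline to the time of response, and to the time of disease progression". No other time point is named, and the time of response is not defined for this purpose.

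**Sampling.**
- Section 6.2 draws blood for XPO1 before dosing and 4 hours "post the first dose of selinexor on cycle 1 day 1 only". Section 6.3 sets the same two times for plasma proteins and cytokines.
- Section 6.1 collects blood for the pathway and apoptosis assays before the first dose, at 24 hours, and then at "cycle 1 day 28 (+/- 7 days), and at progression/relapse (if available"). For marrow, "Bone marrow samples for studies (Vectra, 3-color flow, RPPA, PCR) will be collected at baseline", at cycle 1 day 28 and at progression/relapse if available. Section 7.2.8 repeats this schedule and ties the day 28 marrow to the disease assessment.
- Section 7.2.5 separately orders FLT3 PCR on the clinical marrows at day 28 of cycles 1 and 3, then every 1 to 3 cycles.
- Sections 6.0 and 7.2.8 make the correlative studies optional.

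**Objectives (section 1.3).** Objective 2 concerns FLT3 allelic burden over time in treated patients. Objective 3 concerns biomarker "inhibition and the induction of apoptosis in the bone marrow and peripheral blasts following treatment". Objective 6 concerns the pharmacodynamic effect on XPO1 and on plasma proteins/cytokines.

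**The concern.** The test sentence and the sampling schedule describe different studies. The schedule is built around early fixed times after the first dose, which suits questions about what treatment does to a marker. The test is built around two clinical events whose timing varies by patient, one of which many patients will never reach.

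There are two consequences. Some samples, and one whole objective, are left without a usable planned test, so time points and methods would be chosen after the data are seen. And where the response contrast can be computed, it uses responders only. It then estimates change in patients selected for a good outcome, not change following treatment in treated patients, which is what objectives 2 and 3 ask about.

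**Working it through.** The documents give no sample size, alpha or power for these tests, so there is no stated figure to reproduce. The main check sets the contrasts in section 11.3 against the sampling times.

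| Marker group | Post-baseline samples | Baseline to response | Baseline to progression |
|---|---|---|---|
| XPO1; plasma proteins/cytokines (6.2, 6.3) | 4 h only | Cannot be computed | Cannot be computed |
| Pathway and apoptosis markers, blood (6.1, 7.2.8) | 24 h; cycle 1 day 28; progression/relapse if available | Only for responses seen at day 28 | Yes, if a sample is available |
| Pathway and apoptosis markers, marrow (6.1, 7.2.8) | Cycle 1 day 28; progression/relapse if available | Only for responses seen at day 28 | Yes, if a sample is available |
| FLT3 allele burden (7.2.5) | Day 28 of cycles 1 and 3, then every 1 to 3 cycles | Yes, responders only | Where a marrow is taken |

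Reading down the table:
1. For XPO1 and cytokines the number of usable pairs is 0 by design, however many patients give samples. The only pair available, pre-dose to 4 h, is in no planned test.
2. The 24 h blood sample is in no planned contrast for any patient.
3. Day 28 is used only in patients whose response is seen then. A response first seen at the cycle 3 marrow still counts towards the primary endpoint (section 8.8), but no pathway or apoptosis sample matches it.
4. FLT3 burden has data at response, but that contrast still omits non-responders.

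**Illustrative size.** Inputs: 20 patients per phase II cohort (section 11.0); CRc rates of 35% target and 20% historical (inhibitor-naive cohort), and 20% target and 10% historical (inhibitor-failure cohort), from section 11.2. Full accrual is assumed, and only CRc is counted as response.

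- Expected responders = n × p. Target: 20 × 0.35 + 20 × 0.20 = 7 + 4 = 11 of 40 (27.5%). Historical: 20 × 0.20 + 20 × 0.10 = 4 + 2 = 6 of 40 (15%).
- P(fewer than 5 responders) = Σ C(20,k) p^k (1−p)^(20−k), k = 0 to 4. At target this is 0.12 (naive) and 0.63 (failure).
- Ceiling for a fixed-time contrast: 40 pairs in phase II, or 12 + 2 × 20 = 52 with phase I, if every patient gives the optional samples.
- Smallest standardised paired change d detectable with n pairs: the smallest d for which a noncentral t with n − 1 degrees of freedom and noncentrality d√n exceeds the critical value with probability 0.80. Two-sided 0.05 and 80% power are assumptions.

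| Pairs | Meaning | Detectable change (SD) |
|---|---|---|
| 6 | CRc responders, historical rates | 1.44 |
| 11 | CRc responders, target rates | 0.94 |
| 20 | Fixed time, half of 40 sampled (assumed) | 0.67 |
| 40 | Fixed time, all of phase II sampled | 0.46 |

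The 6 and 11 rows are upper figures for the pathway and apoptosis markers under these assumptions, because only responses seen at day 28 have a sample. The documents do not say what share that is.

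**The case against.** The strongest reply is that the mismatch is partial and the stakes low. Much of it stands.

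- A reader might infer that no samples exist at response or progression. That is wrong. Progression/relapse is a listed time for blood and marrow, day 28 is itself a disease assessment, and FLT3 PCR is run on the marrows on which response is read.
- A reader might infer that every planned test is limited to responders. The progression contrast is not: a patient who progresses without responding can contribute.
- A reader might take the 4 h, 24 h and day 28 samples as available in everyone. They are optional, so 52 pairs is a ceiling.
- Response is not limited to CRc. Section 8 also defines partial remission, morphologic leukemia-free state and hematologic improvement, so the counts of 11 and 6 could be larger. Phase I responders would add to them as well.
- A reader might conclude that the t-test is invalid. Section 11.3 does not say that raw values will be used, and a paired t-test on transformed values fits its wording. The choice of test is secondary to the choice of time points.
- Exploratory objectives can be answered descriptively, so a missing test does not make them unanswerable.
- Fixed-time analysis does not remove selection altogether. Section 7.2.5 lets a marrow be skipped when non-response or progression is clear from blood, so day 28 marrow pairs will also lose some non-responders.

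None of this supplies a contrast for the 4 h or 24 h samples, or for day 28 in all sampled patients. Nor does it change the fact that a baseline-to-response contrast leaves out non-responders.

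**Conclusion.** The point holds in a limited form. Section 11.3 names two contrasts. Neither can be computed for XPO1 or plasma proteins/cytokines, so objective 6 has no usable planned test. The 24 h sample is unused. For objective 3, day 28 enters the response contrast only through responses seen at that visit. For objective 2, data at response exist, but that contrast is restricted to responders while the objective concerns treated patients over time.

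These statements follow from the schedule alone. The sizes (about 11 or 6 of 40 patients in the response contrast, against up to 40 at a fixed time) rest on CRc as the response, full phase II accrual and complete sampling. The detectable changes also rest on assumed alpha and power.

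The sentence should be corrected, but the consequence is confined to exploratory objectives. No primary or secondary analysis, stopping rule or safety decision depends on it.

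**What to change.** Replace the biomarker sentence in section 11.3 with the following plan:

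1. Analyse change from baseline at each scheduled time in all patients with a pair: 4 h for XPO1 and plasma proteins/cytokines; 24 h (blood) and cycle 1 day 28 (blood and marrow) for the pathway and apoptosis markers; each scheduled clinical marrow for FLT3 allele burden.
2. Use a paired test suited to small samples, such as the Wilcoxon signed-rank test.
3. If a response contrast is kept, define the time of response as a named scheduled visit and state which response categories count.
4. Report change at response and at progression/relapse descriptively.
5. At each time, report how many patients gave a pair and how many did not, by response status, because sampling is optional and some marrows may be skipped.

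The cost is SAP wording only. No new samples, visits or patients are needed.
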